3.3 Study design

A two-arm, cluster-randomised controlled trial (level of evidence 1) will be adopted in this study, and conducted as a single-centre study in Switzerland. To reduce potential confounding, the teams will be matched by sex and playing level. All teams will be randomly allocated to a control

or intervention group in a 1:1 ratio. The researcher who conduct the randomization will not be involved in the intervention, and recruitment will be completed before randomization. Computer-generated cluster randomization will be conducted using Research Randomizer software (https://www.randomizer.org/).

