4.3 Study procedures

The observation period will comprise one basketball season from September/October 2021 to May/June 2022. To ensure recruitment of participants, an information sheet containing exclusion/inclusion criteria will be distributed to all basketball teams in August 2021. After signing informed consent forms, eligible participants will be assigned to a control or intervention group in a 1:1 ratio. Teams who meet an acceptance rate of 70% from the roster list will be included in the study.

Data on medical history, age, height, body mass, training characteristics, injury history, basketball experience, and competition level will be collected at baseline. Injury characteristics, including location, type, mechanism, as well as time loss from sport will be reported by the coach or other contact person (therapist, medical doctor) on a weekly injury report form to the researcher (blinded to group allocation) via email (23). For each team, the contact person (preferably, but not necessarily the coach) will be instructed to report injuries that occurred during a scheduled match or training session, causing the player to be unable to complete the current match or training session and/or to fully take part in the next match or training session. If an injury requires medical treatment, basketball player will be instructed to obtain the exact diagnosis from the treating physician. Injury rates will be reported as number of injuries per 1000 athlete exposures. Exposure is defined as one athlete participating in one practice or match. Coaches will register individual playing time (min) and absences (due to an injury) for each training session and match during the season.

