5 STATISTICS

5.1 Statistical analysis plan and sample size calculation

An a priori analysis using G*Power software (version 3.1.7; Heinrich Heine University Düsseldorf, Düsseldorf, Germany) for proportions (using a 2-tailed alpha value of 0.05, and power of 0.80) recommended a sample size of 124 (62 per group), based on previous research (7) reporting a total of 32 injuries (17.5% in intervention group compared to 41.4% in control group) during the 9-month season. The injury incidence rate will be calculated as follows: [(number of events during a specified period)/(total athlete-exposures at risk during a specified period)] x 1000. We will calculate incidence rate ratios together with 95% confidence intervals to assess the risk difference

between the intervention and the control group. The exposure time will be calculated as (1) participation hours and (2) athlete-exposure. The participation hours will be calculated for each group as the sum of the number of exposure hours of each player (match exposure time, training exposure time, total exposure time = match + training hours). The athlete-exposure will be calculated for each group as the number of athletes participating in each game or training session (for example, a team of 10 athletes who participated in 5 games and 50 team practices would accumulate 50 athlete games and 500 athlete practices for a total of 550 athlete-exposures). Differences in participation hours and athlete-exposure between the intervention and control groups will be assessed using the independent t test (if data follows normal distribution) or Mann-Whitney U test (if data does not follow normal distribution). Data analyses will be performed using R. Any deviation from the original statistical plan will be described and justified in the final trial report.

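### Section 5.1 compares exposure between arms with tests for independent observations and does not name the unit; if players are used in this team-randomised trial, the 5% level is generally exceeded

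*Protocol*

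**What the plan says.** Protocol Section 3.3 sets the design: "A two-arm, cluster-randomised controlled trial (level of evidence 1) will be adopted in this study". The team is the unit of allocation ("All teams will be randomly allocated to a control" or intervention group, 1:1), and beforehand "the teams will be matched by sex and playing level".

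Section 5.1 defines exposure in two ways. For hours: "The participation hours will be calculated for each group as the sum of the number of exposure hours of each player". For athlete-exposures, it counts the athletes present at each session and illustrates the count: "a team of 10 athletes who participated in 5 games and 50 team practices would accumulate 50 athlete games and 500 athlete practices", 550 in total. It then fixes the comparison: "Differences in participation hours and athlete-exposure between the intervention and control groups will be assessed using the independent t test", or a Mann-Whitney U test when normality fails.

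Section 4.3 adds that exposure is recorded for individuals: "Coaches will register individual playing time (min) and absences (due to an injury) for each training session and match".

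The protocol does not say whether the observation in the exposure test is the player or the team. It mentions no allowance for team in this test or in any other analysis.

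**The concern.** A two-sample t test and a Mann-Whitney test both take the observations within an arm as independent. Much of a player's exposure comes from the team's calendar. Section 4.1 itself treats training frequency as a team property when it excludes teams that train less than twice a week, and Section 4.2 recruits from three divisions. Teammates' exposures will therefore be correlated.

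The sentence also cannot be carried out as written. One sum per group gives one number per arm and no variance, so the analyst has to choose a unit. Hours are built up from each player and the sample size is counted in players, so the likely choice is the player. That treats roughly 60 correlated values per arm as 60 independent ones. Moving from the t test to Mann-Whitney after a normality check does not remove the dependence.

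At stake is a falsely significant exposure difference, which could be reported as an imbalance between the arms or as an effect of the programme on participation.

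**Working it through.** **Plan's own figure.** None is given for the exposure comparison. The nearest figure is the sample size in Section 5.1: 62 per group for 17.5% against 41.4%, two-sided 0.05, power 0.80. An exact Fisher calculation on independent players gives power 0.796 at 62 per group and 0.805 at 63. So 124 is reproduced to within rounding, with no inflation for clusters. This shows only that the plan counts in players.

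**Inputs.**
- Randomised unit: team (Section 3.3).
- Level: 0.05 two-sided. It is stated for the sample size and assumed here.
- Layout: 6 teams of 10 or 5 teams of 12 per arm. Assumed: each gives 60 players, near the planned 62, and the 10 is borrowed from the counting example.
- ICC of exposure: 0.05 to 0.9. Assumed.
- Correlation ρ between matched teams: 0 to 0.9. Assumed.

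**Step 1: no matching effect.** With m players per team, a player-level test understates the variance of the arm difference by the factor D = 1 + (m − 1) × ICC. Its approximate false-positive rate is 2 × [1 − Φ(1.96/√D)]. For m = 10 and ICC 0.3, D = 1 + 9 × 0.3 = 3.7 and 1.96/√3.7 = 1.02, which gives 30.8%. The simulation used 8,000 runs for the t tests and 2,000 for Mann-Whitney:

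| ICC | D (m = 10) | Closed form | Player t, 6×10 | Player Mann-Whitney, 6×10 | Player t, 5×12 | Team-mean t, 6×10 |
|---|---|---|---|---|---|---|
| 0.05 | 1.45 | 10.4% | 10.9% | 9.5% | 12.1% | 5.1% |
| 0.1 | 1.90 | 15.5% | 15.3% | 14.1% | 18.2% | 4.6% |
| 0.3 | 3.70 | 30.8% | 31.0% | 30.6% | 35.3% | 4.9% |
| 0.5 | 5.50 | 40.3% | 41.9% | 41.0% | 46.8% | 5.0% |
| 0.9 | 9.10 | 51.6% | 53.9% | 51.6% | 59.2% | 5.1% |

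Over both layouts and all ICCs from 0 to 0.9, the t test on team means stayed between 4.6% and 5.4%.

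**Step 2: matching that works.** If matched teams correlate ρ in exposure, the factor becomes D = 1 + [m(1 − ρ) − 1] × ICC. For m = 10, ρ = 0.8 and ICC 0.5, D = 1 + (2 − 1) × 0.5 = 1.5, which gives about 11%. At ρ = 0.9 the bracket is zero and D = 1. The simulated rates are somewhat higher at large ICC. Player-level t test, 6 teams of 10 per arm:

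| ICC | ρ = 0 | ρ = 0.5 | ρ = 0.8 | ρ = 0.9 |
|---|---|---|---|---|
| 0.05 | 10.9% | 7.1% | 5.8% | 4.6% |
| 0.1 | 15.3% | 10.1% | 6.6% | 5.4% |
| 0.5 | 41.9% | 27.9% | 12.9% | 7.0% |
| 0.9 | 53.9% | 41.6% | 21.5% | 10.7% |

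An unpaired t test on team means that ignores effective matching errs the other way. At ICC 0.5 and ρ = 0.8 it rejects in 0.3% of runs.

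**The case against.** The strongest reply is that the unit is unspecified, not wrong. Section 5.1 never says that players are the observations, and its one worked count is a team total. An independent t test on team values is a possible reading, and it would hold its level. This stands. A reader might infer that the planned test is bound to reject far too often, but the protocol supports only the conditional statement: inflation follows if players are the unit.

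Second, a reader might take the counting example, in which all 10 athletes attend all 55 sessions, to mean an ICC of practically 1. It illustrates how exposures are counted and does not estimate within-team variation. Section 4.3 has coaches record individual playing time and injury absences, so hours in particular vary between teammates. This also stands, and the ICC must be treated as unknown.

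Third, matching on sex and playing level may make paired teams' schedules alike. The no-matching figures are then too high, and with a small ICC and very close matching the excess disappears. This stands as a limit on size.

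Fourth, no decision rule in the protocol depends on this p-value, and exposure is already the denominator of every injury rate. That limits the consequence but leaves the reported test without a valid basis on its natural reading.

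**Conclusion.** The point holds as a minor one. Section 5.1 fixes a test for independent observations in a trial that randomises teams, and it leaves the unit open in a way that leads naturally to players. If players are used, the false-positive rate lies above 5% over most of the plausible range: about 11% to 42% for ICC 0.05 to 0.5 without a matching effect, and about 7% to 22% for ICC 0.5 to 0.9 with a matched-team correlation of 0.8 to 0.9. The ICC, the team layout and the matched-team correlation are all assumptions, because the protocol gives none of them. If team values are used, there is no inflation.

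A reader might go further and infer that a spurious exposure difference would undermine the injury rate ratio. The protocol does not support that: the rates are calculated per athlete-exposure, so unequal exposure is already in the denominator. The harm is confined to a misleading supporting p-value.

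**What to change.** In Section 5.1, name the team as the unit of the exposure comparison. For each team, calculate mean participation hours and mean athlete-exposures per player. Compare the arms by a t test or permutation test on team means that respects the matching by sex and playing level. Alternatively, use a mixed model with a team random effect and a small-sample correction. Report the difference with a 95% confidence interval.

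No new data are needed, since exposure is recorded per player and session. The cost is degrees of freedom. In the assumed layout of 6 teams of 10 per arm, a player-level t test claims 2 × 60 − 2 = 118, a t test on team means has 2 × 6 − 2 = 10, and a paired test on six matched pairs has 5. If a within-pair permutation test is chosen, check the number of pairs. Six pairs give 2⁶ = 64 arrangements and a smallest two-sided p of 2/64 = 0.031, but five give 2/32 = 0.0625, which can never reach 0.05.

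Dropping the normality pre-test is optional and separate; it does not affect the dependence between teammates.

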5.2 Handling of missing data and drop-outs

All randomized subjects will be included in the group which they were originally assigned, regardless of adherence to treatment protocol (eg, dropout/withdrawal or protocol deviations). Thus, all data will be analyzed on an intention-to-treat basis. The missing data will replaced with the last observation carried forward.

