3.2 Primary and secondary endpoints

Primary endpoint: Incidence rate of lower extremity injuries

Secondary endpoints:

Incidence rate of ...

- ... overall injuries
- ... severe injuries (lay-off time of more than 28 days)
- ... joint-ligament injuries
- ... muscle injuries
- ... ankle injuries
- ... knee injuries
- ... upper extremity injuries

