8.2 Data recording and source data

Case Report Form (CRF) will be designed in consonance with the Protocol (as a source document), to record data and other information on each trial subject. CRF pages will be identified only by the participant's unique study number to maintain the participant's confidentiality. The principal investigator will retain a confidential master list linking the participants' unique study numbers with participant names; this will be accessible only those working on study data retrieval.

The coaches of each team will be contacted by telephone and/or e-mail once a week to record all training and match activity, in addition to new injuries. Injured players will be interviewed by the injury recorders to assess aspects of the injury based on a standardized injury questionnaire. The injury recorders will be blinded to which group the teams and injured players belong to. If available, the physician's notes (e.g. diagnosis, treatment), imaging reports (e.g. magnetic resonance imaging, computed tomography, musculoskeletal ultrasound), and/or operative notes (e.g. left knee partial medial meniscectomy, left knee arthroscopic anterior cruciate ligament reconstruction with hamstring autograft) will be obtained to confirm diagnoses.

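### Section 5.2 fills missing data by last observation carried forward, which does not fit an injury rate per athlete-exposure: it distorts the arm rates, and also the rate ratio if missingness differs by arm or is related to injury

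*Protocol*

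**What the plan says.** Section 5.2 sets two rules. Players stay in their assigned arm: "All randomized subjects will be included in the group which they were originally assigned, regardless of adherence to treatment protocol". Gaps are filled: "The missing data will replaced with the last observation carried forward". No variable, time point, exception or sensitivity analysis is named.

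The primary endpoint in Section 3.2 is "Incidence rate of lower extremity injuries". Section 5.1 computes it as ["number of events during a specified period)/(total athlete-exposures at risk during a specified period)] x 1000", and adds: "We will calculate incidence rate ratios together with 95% confidence intervals".

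The data behind the rate are repeated records. Section 4.3 has injuries reported "on a weekly injury report form to the researcher (blinded to group allocation) via email", and has coaches log each player's minutes and injury absences at every session. Section 8.2 adds that coaches are contacted "once a week to record all training and match activity, in addition to new injuries". Section 4.3 counts an exposure only when an athlete takes part in a session. The other participant data described in Section 4.3 and the schedule of assessments are taken at screening or baseline.

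**The concern.** Carrying the last observation forward was devised for a state measured repeatedly, such as a score or a weight. A count of new events over accrued time at risk has no such state. Dropout needs no imputation in a rate: when a player leaves, both the injuries and the exposure stop accruing.

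The injury and exposure records are the only repeated outcome data described, and dropouts are kept in the analysis, so these are the records on which the rule would act. Applied there, it puts unobserved exposure into the denominator or, read literally, repeated injuries into the numerator. At stake are the two arm rates, the primary rate ratio and its confidence interval.

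**Working it through.** **No planned figure to reproduce for missing data.** The protocol states no dropout or missing-report rate. Its sample size of 62 per group (17.5% v 41.4%, two-sided alpha 0.05, power 0.80) is reproduced closely by a Fisher exact calculation (power 0.796 at 62 per group, 0.805 at 63). It does not depend on the missing-data rule.

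**Conflict with the protocol's own definition.** Section 5.1 illustrates the denominator with 10 athletes, 5 games and 50 practices: 10 × 55 = 550 athlete-exposures. If one of the ten leaves with *m* sessions remaining, the definition gives 550 − *m*. Carrying that player's participation forward restores 550, so *m* exposures count as "total athlete-exposures at risk during a specified period" although the player was absent.

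**Effect when exposure is carried forward with no injury.** Let *Y* be observed injuries, *E* observed exposure, and *s* the share of the arm's final exposure that is imputed. The completed exposure is *E*/(1 − *s*), so:

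- arm rate after the rule = (1 − *s*) × *Y*/*E*
- rate ratio after the rule = observed rate ratio × (1 − *s* intervention)/(1 − *s* control)

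The shares below are assumptions:

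| Imputed share, intervention | Imputed share, control | Factor on rate ratio |
|---|---|---|
| equal | equal | 1.00 |
| 15% | 5% | 0.85/0.95 = 0.89 |
| 5% | 15% | 0.95/0.85 = 1.12 |

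If a fraction *d* of players leaves at uniformly random weeks, *s* is about *d*/2. Shares of 15% and 5% therefore correspond to 30% and 10% of players leaving.

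**Simulation check.** Assumed: 62 players per arm, 36 weeks, 3 athlete-exposures per week, 0.414 injuries per control player-season, true ratio 0.175/0.414 = 0.423, Poisson counts, no clustering. The control rate is then 0.414/(36 × 3) × 1000 = 3.83 per 1000.

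- Zero-injury carry-forward, 20% leaving in both arms: rates fall from 3.82 to 3.44 (control) and from 1.62 to 1.46 (intervention). The ratio stays at 0.41.
- Zero-injury carry-forward, 30% intervention and 10% control leaving: ratio 0.404 becomes 0.361. Reversed: 0.410 becomes 0.458. Both agree with the formula.
- Injury and exposure both carried forward, 20% leaving at random in both arms: mean rates hardly move (3.82 to 3.81 and 1.62 to 1.64), but the SD of the log ratio rises from 0.42 to 0.54.
- Counting only observed injuries and exposure: the ratio stays at 0.40 to 0.42 in every scenario, near the true 0.423.

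**Confidence interval.** With zero-injury carry-forward the spread of the log ratio barely changes (SD 0.417 v 0.420). The interval keeps about the same width on the log scale, centres on the shifted estimate, and makes no allowance for the imputed exposure. If injuries are repeated, each copy counts as a separate event, so the nominal interval narrows while the true variability grows.

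**The case against.** The sentence in Section 5.2 is generic. An analyst could give precedence to the at-risk denominator in Section 5.1 and never impute exposure. A separate analysis plan might narrow the rule. Weekly contact with every team's coach should keep gaps small. If the last record is a week without participation, carrying it forward adds no exposure. All of this is fair and limits the likely damage. It does not remove the conflict: the protocol fixes a method that, followed as written, breaks its own exposure definition.

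Three stronger readings are tempting but not supported.

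- *The rule biases the rate ratio in the programme's favour.* Bias in the ratio needs missingness that differs by arm or is related to injury, and it can run either way. Section 4.4 allows withdrawal for non-compliance, and only intervention teams take on a new programme, so a difference between arms is conceivable. Nothing in the protocol shows it to be likely.
- *The distortion is 16% or more.* A factor of 0.80/0.95 = 0.84 needs 20% v 5% of exposure imputed, hence about 40% v 10% of players leaving at random weeks. The protocol gives no such rates.
- *A player who leaves injured with 20 weeks left adds 20 injuries, against 62 × 0.414 = 25.7 in the control arm.* A laid-off player is recorded as absent under Section 4.3, not missing, and Section 8.2 asks for new injuries. The example needs the player to leave observation entirely and the analyst to recount one injury every week. Moreover, 25.7 is a number of injured players from a calculation for proportions, and is not stated to concern lower extremity injuries. On that extreme literal reading, with 10% to 30% of injured players leaving, the simulated control rate does rise about 2.8 to 6 fold, but this is not the expected outcome.

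**Conclusion.** The point stands as a wrong method stated in the protocol, not as a missing detail. Unrestricted carry-forward contradicts the definition of exposure as participation. It lowers the arm rates by the imputed share or, on the literal reading, inflates the variance. Bias in the rate ratio is conditional: none with equal missingness unrelated to injury, and a factor of about 0.89 or 1.12 if 15% and 5% of exposure are imputed in one direction or the other. Those shares are illustrative assumptions, and the simulation ignores team clustering. That the rule is unsuitable is certain; the size and direction of its effect on the primary result cannot be determined from the protocol.

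**What to change.** Remove the carry-forward sentence from Section 5.2 for injury and exposure data. In its place, state that injuries and athlete-exposures are counted for each player over the period actually reported, with exposure as the denominator or as a log offset, in an analysis that respects the randomised teams. Keep the rule that players are analysed in their assigned arm.

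Add one sensitivity analysis for missing team-weeks, for example imputing them at the team's own rate and schedule, then at a less favourable rate for intervention teams. Where a weekly report is missing, the coach's session register may fill the gap, although it comes from the same source. Report the share of missing player-weeks by arm, so that the factor above can be evaluated with real figures.

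The synopsis dates this version 28.09.2022 and the last participant out 30.06.2022, so the change concerns analysis only. If it comes after the plan is final, Section 5.1 already requires deviations to be described and justified in the final report. The cost is one rewritten sentence, one extra analysis and slightly less exposure in the primary analysis. The sample size is unaffected.

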6 REGULATORY ASPECTS AND SAFETY

6.1 Local regulations / Declaration of Helsinki

The study protocol will be approved by the regional ethics committee (Ethikkommission Nordwestund Zentralschweiz) and conducted in compliance with the Declaration of Helsinki.

6.2 (Serious) Adverse Events

Considering the role of the feedback in effective teaching motor skill and neuromuscular control, intervention-related foreseeable risks and/or discomforts (physical) that could reasonably be anticipated are lower than those encountered in regular training and competition (A category according to ClinO, Art. 61). Participant may experience one or more of the risks indicated below from participating in this study:

- There is a risk for injury (related to the trial intervention: possibly; severity: mild) if proper form and technique are not utilized. The risks will be minimized by focusing on proper technique, movement awareness, body positioning and basketball-specific activity demands, along using trained technicians (e.g. strength and conditioning coaches) as well as research participants that have experience with neuromuscular training.
- After exercise, muscle soreness (related to the trial intervention: possibly; severity: mild) may be present for the next 24-48 hours.

There may be other unknown risks, or risks that we do not anticipate, associated with participation in this study.

Reporting of SAEs (see ClinO, Art. 63)

An AE that meets the criteria for a SAE will be documented and reported immediately (within a maximum of 24 hours) to the investigator of the study as an SAE. If it cannot be excluded that the SAE occurring in Switzerland is attributable to the intervention under investigation, the Investigator will report it to the Ethics Committee via BASEC within 15 days. Since only healthly participants will be recruited, SAEs will not be exempted from expedited reporting.

Follow up of (Serious) Adverse Events

All SAEs will be followed until resolution, or until the condition has stabilized with no further change.

6.3 (Periodic) safety reporting

After study termination, an annual safety report (ASR/DSUR) will be submitted to the local Ethics Committee by the Investigator (ClinO, Art. 43 Abs).

